Royston Parmar flexible parametric survival models will be used to estimate the hazard ratio of severe COVID-19 outcome (hospital or critical care admission and death) in cohort 1 for patients with neuropsychological disease at study entry compared with those without disease, and for individual neuropsychological diseases and treatments.

This analysis will be adjusted for the listed covariates. The age variable will be included as a restricted cubic spline rather than a linear term. Before commencing analysis, we will assess the numbers of patients with each comorbidity, and may if necessary group the presence of certain less common comorbidities together. Any such grouping will be done on the basis of clinical similarities only and prior to examining any outcomes by comorbidity. We may also include a time-varying binary covariate to record any new diagnosis and/or treatment which occurs after study entry in patients originally free from both diagnosis and treatment, depending on the number of these events. Proportional hazards assumptions will be tested, and time dependent terms will be included if the hazard ratio changes over time (I.e. if the association between neuropsychological disease and risk of severe COVID-19 has changed during the course of the pandemic). A random frailty term will be included to account for similarities amongst patients registered in the same primary care practice. Possible interactions between exposure and age, sex and ethnicity will be considered and tested using a Wald test.

The same methods will be used for secondary analyses in which the main exposure variable will be defined as either the presence of a specific class of neuropsychological disorder or any other neuropsychological disorders or no disorder.

The primary analysis will be used to estimate the hazard ratio of severe SARI outcomes in cohort 2 using the same exposure variables.

If non-proportional hazards are observed in either cohorts 1 or 2, then maximum follow-up time will be capped at 1 year and a time-dependent covariate will be added to the analysis of both cohorts to maintain the comparability of results.

Aim 2.

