Cause-specific Royston Parmar flexible parametric models will be used to estimate the hazard ratios of developing new neuropsychological diseases after having received intensive care, comparing patients who received intensive care for COVID-19 (cohort 3) vs those who received intensive care for SARI (cohort 4). This model will adjust for all previously listed covariates. The age variable will be included as a restricted cubic spline rather than a linear term. Follow-up will start on the date of discharge from hospital.

Proportional hazards assumption will be tested, and time dependent terms will be included if the hazard ratio changes over time. A random frailty term will be included to account for similarities amongst patients admitted in the same critical care unit

A limited number of two-way interactions which are considered to be clinically or biologically plausible will be identified prior to analysis, and tested using a Wald test.

Primary care data on some potential confounding variables is incomplete (e.g. smoking status, alcohol intake, ethnic group, BMI). Reason for admission is mandatory for all records in the ICNARC database (the core dataset for aim 2), so classification of these reasons as either SARI or COVID related will be non-missing for all patients. Only admission records for completed critical care stay (non-missing length of stay and survival status at end of critical care) will be included (n.b. outcomes are missing in <1% of COVID ICU admissions to date). Remaining variables from the critical care stay are use of sedation in the first 24 hours, and duration of advanced respiratory support, which are missing for a small number of patients (<1.5%).

Both aims.

To allow data analysis with all eligible patients, we will impute missing data in all cohorts. We will use multiple imputation with chained equations under the missing at random assumption to replace missing values and use these values in our main analyses [15]. We will include all exposure and confounding variables in the imputation model, along with the Nelson–Aalen estimator of the baseline cumulative hazard, and the outcome indicator. We will carry out five imputations. Analysis models will be fitted in each imputed dataset and Rubin's rules to will be used to combine the results across the imputed datasets.

As the analyses are on time to event data, patients will be censored at the date when they are lost to follow-up as defined in cohort definitions above.

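### The imputation model, as listed, omits the exposure-by-outcome terms that the planned exposure-by-ethnicity test needs, so the interaction estimate shrinks by roughly the share of ethnicity that is missing

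*Protocol*

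**What the plan says.** Under Statistical Methods, Aim 1, the protocol states: "Possible interactions between exposure and age, sex and ethnicity will be considered and tested using a Wald test". The same methods carry over to the secondary analyses by class of disorder.

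At the end of the Aim 2 text it states: "Primary care data on some potential confounding variables is incomplete (e.g. smoking status, alcohol intake, ethnic group, BMI". The Covariates section gives ethnicity eight groups. Unlike smoking and alcohol, it has no level for unrecorded values, so imputation is the only stated main-analysis handling of missing ethnicity.

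Under Both aims, the method is chained equations assuming data missing at random, with the imputed values used in the main analyses. On contents: "We will include all exposure and confounding variables in the imputation model", together with the Nelson-Aalen cumulative hazard and the outcome indicator. On number: "We will carry out five imputations". Results are pooled by Rubin's rules. Product terms and imputation within exposure groups are neither mentioned nor ruled out.

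For Aim 2: "A limited number of two-way interactions which are considered to be clinically or biologically plausible will be identified prior to analysis". None is named. Sensitivity analyses plans a complete-case analysis but does not tie it to the interaction tests.

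**The concern.** An imputation model has to be at least as rich as the analysis model fitted afterwards. Including the outcome indicator and the Nelson-Aalen term protects the main effects of an imputed covariate. It does not protect an interaction between that covariate and the exposure. For that, the model for ethnicity must allow the link between ethnicity and outcome to differ by exposure level.

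If the listed variables enter as main effects only, the imputed records are generated as though the exposure effect were the same in every ethnic group. Mixing them with the observed records dilutes any real difference. At stake is a named effect-modification analysis, which could report little or no difference by ethnicity because of how the gaps were filled.

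**Working it through.** **Inputs from the protocol.** The contents of the imputation model, five imputations, Rubin's rules, incomplete ethnicity, the Wald test of exposure by ethnicity, and about 8.3 million adults for Aim 1. The protocol gives no missing fraction, event risk, exposure prevalence, interaction size or power, so there is no figure of its own to reproduce. Everything else below is an assumption.

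**Why the interaction vanishes in imputed records.** Take a binary ethnicity E, exposure X, event indicator D and Nelson-Aalen value H. The list read as main effects gives

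logit P(E = 1 | X, D, H) = a + bX + cD + gH.

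The log odds ratio between E and X is then b whether D is 0 or 1, so the X-by-D-by-E association is zero. With a rare outcome that association approximates the log ratio of hazard ratios, θ. If a fraction f of ethnicity is imputed, the pooled estimate should be near (1 − f)θ. For a true ratio of 1.40, θ = ln 1.40 = 0.3365, which predicts:

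- f = 10%: exp(0.9 × 0.3365) = 1.35
- f = 20%: exp(0.8 × 0.3365) = 1.31
- f = 30%: exp(0.7 × 0.3365) = 1.27
- f = 40%: exp(0.6 × 0.3365) = 1.22

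**Simulation with survival times.** 60,000 patients; 200 replicates per setting; minority share 15%; exposure 18% to 25%; exponential event times; follow-up up to 1.43 years; reference-group hazard ratio 1.5 and minority 2.1 (ratio 1.40); ethnicity missing completely at random; five imputations; Rubin's rules; two-sided 5% Wald test. The compatible model adds X × D and X × H.

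| Missing | Ratio, as listed | Share of θ recovered, as listed | Ratio, compatible | Rejection rate, as listed | Rejection rate, compatible |
|---|---|---|---|---|---|
| 10% | 1.36 | 92% | 1.40 | 0.73 | 0.79 |
| 20% | 1.31 | 81% | 1.40 | 0.55 | 0.68 |
| 30% | 1.27 | 71% | 1.42 | 0.37 | 0.64 |
| 40% | 1.22 | 58% | 1.38 | 0.21 | 0.55 |

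The as-listed ratios match the prediction, and attenuation runs from 100 − 92 = 8% to 100 − 58 = 42%. With 200 replicates the Monte Carlo standard error of a rejection rate is at most √(0.5 × 0.5 / 200) = 0.035.

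**Missing at random.** In one setting with about a quarter missing, and less missing among exposed patients and events, the as-listed model recovered 81% and the compatible model 96%.

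**No true interaction, 30% missing, 400 replicates.** The as-listed model rejected in 0.5% and the compatible model in 5.2%. The low rate arises because the as-listed model's average Rubin standard error (0.153) exceeds the actual spread of its estimates (0.112). The effective cut-off is 1.96 × 0.153 / 0.112 = 2.68, a two-sided level of about 0.7%.

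**Second simulation, built differently.** 8.3 million patients as grouped counts; 600 replicates; one ethnic group of 2%; exposure 20%; event risk 0.5%; true ratio 1.20; logistic models. At 10/20/30/40% missing:

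- Attenuation was about 8/20/28/40%, so 1.20 became 1.18/1.16/1.14/1.12.
- Power was 79/64/48/27% as listed, against 84/79/71/67% with the exposure-by-outcome term.
- Rejection under no interaction at 30% missing was again about 0.5%.

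**The case against.** The strongest reply is that the protocol names the variables that enter the imputation model and not its functional form. Product terms are ordinary detail for a statistical analysis plan, which may exist and may supply them. This stands in part: it would be wrong to say that the protocol prescribes a model without interactions. But the imputation paragraph does more than defer. It fixes method, assumption, contents, number and pooling, and anyone who follows its list arrives at the attenuated estimate.

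A second reply is sample size. With 8.3 million adults some power may be recovered, but the bias stays: the estimate settles on roughly (1 − f)θ however many patients there are.

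A third is that the complete-case analysis would expose the problem. In the survival simulation complete cases did recover 96% to 102% of the true log interaction, though with a single incomplete covariate. The safeguard is real only if the interaction test is repeated there, which the protocol does not say.

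Several stronger readings are tempting, and the protocol does not support them:

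- A reader might infer that planned ethnicity-specific hazard ratios are pulled toward 1. None is planned, and they would move toward each other: at 30% missing, true values of 2.0 and 1.0 became 1.94 and 1.22, so one moved away from 1.
- A reader might infer that Aim 2 is equally affected. No Aim 2 interaction is named, and smoking and alcohol have their own unrecorded category, so whether they would be imputed is unclear.
- A reader might infer spurious findings or biased primary results. The test rejects too rarely, and nothing here shows bias in the main-effect hazard ratios. Age and sex, the other two Aim 1 modifiers, are not named as incomplete.

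**Conclusion.** The point holds in this limited form. The imputation model as listed does not fit the planned exposure-by-ethnicity test. Used as written, it biases the interaction toward none by roughly the missing fraction, about 8% to 42% on the log scale for 10% to 40% missing. At 30% missing the nominal 5% test rejects about 0.5% of the time when there is no interaction, and power for a true ratio of 1.40 falls from 0.64 to 0.37 in the survival simulation.

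The direction and approximate proportionality follow from the structure of the model, and two differently built simulations agree on them. The power figures are illustrative. They depend on assumed missingness, a two-group ethnicity and a binary exposure, whereas the protocol has eight groups and a three-level exposure. At 10% missing the power loss is only 5 to 6 points (84% to 79%, and 0.79 to 0.73). For Aim 2 the point is conditional on choosing an interaction with an imputed covariate.

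**What to change.** In Statistical Methods, Both aims, state that for every interaction to be tested with an incomplete covariate, the imputation models will include exposure-by-outcome-indicator and exposure-by-Nelson-Aalen terms. Running the chained equations within exposure groups, or using substantive-model-compatible imputation, would serve equally. In the survival simulation the product terms recovered 96% to 103% of the true log interaction in every setting with a real interaction. For Aim 2, apply the same rule once the interactions have been chosen.

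In Sensitivity analyses, state that the interaction tests will be repeated in complete cases.

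The cost is two sentences and some extra computing. Where an exposure category is rare, imputing within groups may leave strata too small, and the product-term version may be needed.

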 Cohort one is adult patients aged 18 years of age or over on 24th January 2020 (the study entry date, when the first confirmed COVID-19 case occurred in the UK) who were registered in a primary care practice within the QResearch programme on or before 24th January 2019. Patients will be followed-up from study entry date until development of severe COVID-19 disease, defined as the first date of either hospitalisation, ICU admission, or death. Patients will be censored at the first occurrence of deregistration from the GP practise, death, or date of the final data extract from the linked datasets.

Cohort two is an open cohort of patients aged 18 years of age or over (including those who become 18 within this period) who had been registered with a primary care practise within the QResearch database for at least one year, between 24th January 2015 and 23rd January 2020. For each patient, the earliest day on which all these conditions were met will be defined as their study entry date, and they will be followed-up until development of severe disease due to SARI, defined as hospitalization, ICU admission, or death. Patients will be censored at the earliest of first occurrence of deregistration from the GP practise, death from other causes, 24th January 2020 or date of the final data extract from the linked datasets.

Aim 2.

- Cohort three will include adult patients (aged 18+ on date of hospital admission) discharged alive following a hospital admission including an ICU admission resulting from COVID -19 infection (defined below) between 24 January 2020 and study end date, who were registered in a primary care practice within the QResearch programme before their ICU admission. It will be used to evaluate the risk of subsequent neuropsychological sequalae from the date of discharge. Patients will be censored at the earliest of first occurrence of deregistration from the GP practice, death from other causes, 12 months post discharge from hospital, or date of the final data extract from the linked datasets.

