- Cohort four will include adult patients (aged 18+ on date of hospital admission) discharged alive following a hospital admission including an ICU admission resulting from SARI (defined below) admitted between 24 January 2015 and 23rd January 2020, who were registered in a primary care practice within the QResearch programme before their ICU admission. The cohort will allow comparisons to be made with cohort three. Follow-up will be from the date of discharge. Patients will be censored at the earliest of first occurrence of deregistration from the GP practise, death from other causes, 12 months post discharge from hospital or date of the final data extract from the linked datasets.
- Cohort 5 will include adult patients (aged 18+ on date of hospital admission) discharged alive following a hospital admission including an ICU admission resulting from SARI (defined below) between 24 January 2020 and study end date, who were registered in a primary care practice within the QResearch programme before their ICU admission. It will be used to allow comparison with cohort 3. Patients will be censored at the earliest of first occurrence of deregistration from the GP practice, death from other causes, 12

months post discharge from hospital, or date of the final data extract from the linked datasets.

Variables

Definition of outcomes Aim 1

For cohort one, our primary outcome is the first occurrence of any one of the following:

1. Hospital admission resulting from COVID-19 infection defined as testing positive for SARS-CoV-2 (as recorded in the PHE database) in the 14 days prior to or during a hospital admission period in the HES dataset, or having an ICD10 code U07.01 for confirmed COVID-19 diagnosis in that HES admission record

2. Admission to an ICU resulting from COVID-19 infection which will be defined as patients admitted to an ICU within the ICNARC dataset of COVID-19 admissions.

3.All - cause mortality following COVID-19 infection.

Secondary outcomes are each of the three events defined above, considered separately (i.e. COVID-19 hospital admissions; ICU admission; death).

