- oral steroids

Intensive care stay (Aim 2)

- Length of stay
- Duration of advanced respiratory support (invasive ventilation)
- Use of sedation in the first 24 hours of admission

Effect Modifiers

For aim 1, we assessed these potential confounders by creating directed acyclic graphs (DAG) to determine which variables were likely to be to some extent caused by the presence of prior neuropsychological disorders (as the exposure of interest), and which were not likely to be caused by the presence of prior neuropsychological disorders, but were thought to be independently potential predictors of severe Covid outcomes.

Variables from the above list to be included in the model are all those grouped under: demographics; co-morbidities; lifestyle factors; plus prescription of any immunosuppressants and/or anticoagulants. Other medications (as these are not believed to affect the risk of severe Covid outcomes), and in-hospital factors (length of stay and use of sedation during intensive care admission, as these are outcomes potentially caused by Covid severity) will not be adjusted for.

For aim 2, our exposure of interest is admission to intensive care with SARI (compared to admission to intensive care with SARI. This exposure occurs at a fixed time which is used as the baseline for our time to event analysis in predicting the outcome of interest, and all other variables listed above are measured before this baseline. Therefore (depending on the available sample size and number of events), all the previously listed covariates of interest may be included in our adjusted models.

Data sources

Intensive Care Unit admission data will come from the ICNARC CMP dataset Hospital admission and mortality will come from the HES dataset

All exposures and confounders and neuropsychological outcomes will come from the QResearch database.

COVID-19 infection test status will come from the national registry of COVID-19 RT-PCR positive test results from Public Health England (PHE).

Bias

To limit the possible impact of COVID-19 testing bias (collider bias) we will analyse the entire QResearch eligible population, rather than restricting analysis to only those with a positive COVID-19 test.

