For aim 1, the various different neuropsychological conditions of patients in cohort 1 are likely to result in varying levels of exposure to covid-19, compared to the populations without these conditions, with some conditions likely to have a protective effect, but in other conditions the reverse is expected. We have added a secondary analysis to examine the effect of specific conditions in order to evaluate this.

For aim 2, the two cohorts have experienced their exposure of interest (ICU admission with either COVID or SARI) during different time frames. Patients with SARI (admitted to ICU between 2015 to 2020) will have longer follow-up, but patients with COVID (admitted to ICU during 2020/21) may have benefited from the recently increasing public awareness of mental health conditions. To combat this, we have capped all follow-up at a maximum of 1 year post ICU discharge, and we will include a time-dependent covariate to assess whether risk varies with time post discharge. We have also included a cohort of patients with SARI admitted during 2020/21 for comparison with the COVID cohort during the same time frame.

We will derive the E-value to estimate the extent unmeasured confounding.

Study Size

For aim 1 we will use the entire QResearch database of approx. 8.3 million adult patients to maximise precision and minimise selection bias. We chose to use the last 5 years of ICNARC data for SARI comparisons to use recent data whilst having sufficient numbers for comparison taking into account the numbers from previous studies and after linkage [13, 14].

For aim 2, we will use all known ICU admissions from the ICNARC database for SARI and/or COVID who can be linked to the QResearch database. In cohort 3 the expected sample size is in the region of 11,000 admissions in total, for cohort 4 it is likely to be in the region of 7,000 admissions per year, and for cohort 5 around 3,500 patients.

Quantitative variables

Quantitative variables will be treated as continuous variables without categorisation. Descriptive summary statistics (mean and standard deviation, median interquartile range or number (%) as appropriate) will be used to present sociodemographic and clinical characteristics of patients with and without COVID-19 infection for those with and without neuropsychiatric conditions or treatments.

Statistical Methods

Aim 1.

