Sensitivity analyses

We will undertake complete case analysis in those without missing data as a sensitivity analysis of our findings.

We will also restrict analysis to only include patients with confirmed COVID-19 diagnosis using RNA testing.

For Aim 2 we will carry out a sensitivity analysis in cohort four with additional censoring of follow-up on 24th January 2020, so that outcomes are assessed prior to the pandemic period. In comparing cohort 3 and 4 we will consider the competing risk of death by undertaking a competing risk analysis.

In order to compensate for the low expected event rates relative to our sample sizes for aim 2, we will combine cohorts 3 and 4 and use all available baseline characteristics (as listed previously) to calculate a propensity score to measure the likelihood of developing a new neuropsychological condition up to 1 year after ICU admission. We will then use these scores (with inverse probability weighting) to compare the adjusted hazard of developing a new neuropsychological condition in patients admitted to critical care for COVID compared to those admitted for SARI.

The authors will have full access to anonymised data from the Case Mix Programme, QResearch and Public Health England, and Hospital Episode statistics databases. We will remove duplicate records for the same individual, and set dates and values outside a pre-defined credible range as missing. For patients admitted with SARI between 2015-2020 the full set of standard data validation processes for unit level data intended for public reporting will have been carried out by ICNARC. Some of the more recent Covid admissions will have undergone a more restricted set of validations, but these do include confirming the total number of admission with Covid to each unit, checking that duration of organ support does not exceed duration of stay, and confirming with units that that aggregated units level summaries of length of stay and organ support (among other measures) are in line with expectations. All variables used in the analysis will be initially summarised in a table of baseline characteristics to include minimum, maximum, median and quartiles.

Data linkage

Person-level data linkage will be undertaken between QResearch, Hospital Episode Statistics, the Case Mix Programme and Public Health England. Cases will be matched on pseudonymised NHS number [15].

Discussion

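### As worded, the RNA-confirmed sensitivity analysis selects the Aim 1 population on a positive test, so it is not a valid robustness check of the primary result

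*Protocol*

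**What the plan says.** The Bias section of the Protocol sets out the main safeguard: "To limit the possible impact of COVID-19 testing bias (collider bias) we will analyse the entire QResearch eligible population". It names the alternative that it turns down; the full population is used "rather than restricting analysis to only those with a positive COVID-19 test". The Study Size section is consistent with this: "For aim 1 we will use the entire QResearch database of approx. 8.3 million adult patients".

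The Sensitivity analyses section adds, as a sentence on its own: "We will also restrict analysis to only include patients with confirmed COVID-19 diagnosis using RNA testing". It does not name the aim or cohort. It does not say whether the population or the case definition is restricted, when follow-up starts, or how a difference from the main result would be read.

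Three other statements bear on it:

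- **Time origin (Participants, Aim 1, cohort one).** Study entry is 24 January 2020 for everyone, and "Patients will be followed-up from study entry date until development of severe COVID-19 disease".
- **Outcome (Definition of outcomes, Aim 1).** A COVID-19 hospital admission counts if there is a positive test "in the 14 days prior to or during a hospital admission period in the HES dataset". A second route needs no test result: "or having an ICD10 code U07.01 for confirmed COVID-19 diagnosis in that HES admission record". An admission can therefore qualify on its code alone.
- **Exposure and infection (Bias).** The neuropsychological conditions are described as "likely to result in varying levels of exposure to covid-19, compared to the populations without these conditions", with the direction expected to differ between conditions.

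**The concern.** The sensitivity analysis appears to carry out, for Aim 1, the restriction that the Bias section says is avoided, and it does not acknowledge the tension.

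Conditioning on a positive test biases a comparison when both exposure and outcome influence who tests positive. The Protocol supplies both links. Infection exposure differs by condition, and the outcome admission can itself produce the test. Restricting to test-positives also changes the question, from the risk of severe COVID-19 in the population to the risk of severe disease among people who tested positive.

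A reader will take this analysis as a check on the primary hazard ratio. If the two differ, the gap could come from testing patterns or from the change of question, and would wrongly count against the primary finding. If they agree, the agreement could be coincidental and would wrongly count in its favour.

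**Working it through.** The Protocol gives no testing rates and no figure tied to this analysis, so there is nothing of its own to reproduce. The check has three parts.

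**1. The statements compared.** The Bias section rejects restriction to people with a positive test. The Sensitivity analyses section restricts to patients with an RNA-confirmed diagnosis. For Aim 1 these are the same set of people if the sentence is taken as a rule about who is included. No other start of follow-up is given for it. If 24 January 2020 is carried over, patients enter the analysis because of a test that happens later.

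**2. Selection when exposure has no effect.** Assume exposure changes neither infection nor severity. All inputs are assumptions:

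- s = P(severe | infected): 0.02 to 0.10
- ts = P(test-positive | severe): 0.95 in both groups
- t0 = P(test-positive | infected, not severe, unexposed): 0.1 to 0.6
- t1 = the same in the exposed, with t1/t0 from 0.67 to 1.5

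Among test-positives in each group, with t set to t0 or t1:

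P(severe | positive) = s·ts / [s·ts + (1 − s)·t]

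Worked case, s = 0.05 and t0 = 0.3:

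- Unexposed: 0.0475 / (0.0475 + 0.285) = 0.143
- Exposed, t1 = 0.67 × 0.3 = 0.201: 0.0475 / (0.0475 + 0.191) = 0.199, risk ratio 1.39
- Exposed, t1 = 1.5 × 0.3 = 0.45: 0.0475 / (0.0475 + 0.4275) = 0.100, risk ratio 0.70

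Risk ratio among test-positives when the true value is 1.00:

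| s | t0 | t1/t0 = 0.67 | 0.8 | 1.0 | 1.25 | 1.5 |
|---|---|---|---|---|---|---|
| 0.02 | 0.6 | 1.47 | 1.24 | 1.00 | 0.81 | 0.67 |
| 0.05 | 0.3 | 1.39 | 1.21 | 1.00 | 0.82 | 0.70 |
| 0.10 | 0.1 | 1.19 | 1.11 | 1.00 | 0.89 | 0.80 |

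The first and last rows hold the widest and narrowest spreads over the grid, so the overall range is about 0.67 to 1.47.

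If everyone stays at risk and the RNA requirement is placed on the outcome instead, the ratio is (s·ts)/(s·ts) = 1.00 in every scenario. This relies on severe cases being tested equally in the two groups.

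**3. Change of question.** Suppose exposure changes infection risk by a factor of 0.7 to 1.5, does not change severity, and testing is equal. The whole-population risk ratio is then 0.7 to 1.5, while the ratio among test-positives is 1.00. The two analyses can disagree with no testing bias at all, because they estimate different quantities.

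**The case against.** **The sentence may mean something else.** Admissions can count on a diagnosis code without a positive test, so the sentence could mean dropping code-only cases from the outcome or from cohort 3. That is an ordinary and legitimate misclassification check. This stands as a possible reading, and for Aim 2 the restriction is unobjectionable: everyone there is already a hospital or ICU patient, so the whole-population argument does not carry over directly. For Aim 1 the wording limits which patients are included, so the literal reading is restriction of the population.

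**The Bias section governs the main analysis.** It speaks of limiting a possible impact, and the main analysis keeps the whole population. A reader might infer that the Protocol undoes its own safeguard or that the primary result is compromised. Neither follows. A restricted result may be shown beside a whole-population one if it is labelled for what it is.

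**Follow-up time.** A reader might infer that time before the test is event-free by construction. That is not strictly so: a test taken during the admission qualifies, so the event can precede the test. The start date for this analysis is also unstated, and a statistical analysis plan may set it. What stands is conditional: if 24 January 2020 is kept, the analysis selects on a later event.

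**Size.** Every input is assumed, and the figures are unadjusted, whereas the model adjusts for domicile, including care home residence, which could remove part of any testing difference. More extreme inputs give more dramatic results: with s = 0.05, ts = 0.95, t0 = 0.2 and t1 = 0.6, the ratio is 0.077/0.200 = 0.38. Nothing in the Protocol supports a threefold difference or fixes its direction.

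**No value at all.** A reader might conclude that such an analysis can never be informative. That is too strong. The selection bias illustrated here disappears if testing of non-severe infections does not differ by exposure given the covariates, and severity after a positive test is a reasonable question in its own right.

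**Conclusion.** The point holds for Aim 1 on the literal wording. The analysis makes the selection that the Bias section sets aside, answers a different question from the primary analysis, and can move in either direction through testing alone. The illustrative range of about 0.67 to 1.47 under a true null shows that the effect can be material; it does not estimate the bias in this study. It rests on the assumed severity and testing probabilities, on severe cases being tested equally in both groups, and on no covariate adjustment.

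As written, the analysis is not a valid robustness check of the primary result. The primary whole-population analysis is unaffected, and restricting cohort 3 to RNA-confirmed cases for Aim 2 is acceptable. The sentence should be changed, but the defect is confined to a secondary analysis.

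**What to change.** Replace the sentence in Sensitivity analyses with one that names the aim and the object of the restriction:

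- **Aim 1.** All of cohort 1 stays at risk from study entry. Only severe events confirmed by RT-PCR count as outcomes; events identified by code alone are not counted.
- **Aim 2.** Cohort 3 is restricted to RT-PCR-confirmed admissions.
- **Optional.** If an Aim 1 analysis of test-positive patients is still wanted, start follow-up at the positive test. Describe it as severity given a positive test, exposed to testing selection, and do not present it as a robustness check.

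This uses the linked data already planned and leaves the primary analysis as it is. The cost is fewer events in this sensitivity analysis; the Protocol does not give the share of code-only events, so the loss cannot be sized.
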